3.3 Procedure

The study was conducted by two expert pediatric dentists. One of them gave all explanation, spoke with the children and carried out the anesthesia procedure and did the treatment procedure [name] and the other [name] was observing and assessing the children's pain perception.

In this study's cross-over design, children received both types of injections before filling/pulpotomy treatment on their maxillary primary molars in two separate appointments with a minimum interval of at least 1 week between procedures, on a side of the dental arch with the use of a needle free injection and on the other side with the traditional syringe. Type and sequence of administration to each individual were randomly assigned (using a coin). All dental equipment were introduced using 'tell-show-do technique. A total of 56 procedures were performed and divided into 2 groups according to the anesthesia technique. None of the children have undergone any previous dental local anesthetic experience, in order to be not influenced by a positive or negative memory.

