3.4 Data collection

A structured form was designed to collect information regarding

- (1) patient's age;
- (2) gender;
- (3) type of teeth injected
- (4) type of dental treatment (filling or pulpotomy);
- (5) total amount of local anesthetics (LAs) used (ml)
- (6) duration of the analgesia effect (min)
- (7) post-op pain (after one day)
- (8) score on WB PRS after injection
- (9) score on FLACC during injection.

The Effect of Needle-free Injection System on Dental Injection Pain in Children: A Cross-over, Randomized Clinical Trial

Statistical Analysis

Post hoc power analysis was conducted for the study and the results of the comparison between the injection systems and Wong Baker scores were evaluated. According to this, with a total data set of 28 individuals, consisting of two independent groups and two dependent measurements, the power of the study was found to be 0.94 according to the G*Power 3.9.1.4 program, based on the partial eta squared (η^2) value of 0.108 obtained with a 0.05 error margin from the repeated measures ANOVA. The data were statistically analyzed using SPSS software (version 15.0, SPSS). Paired t-tests or Wilcoxon nonparametric tests were used to compare data within groups over two time periods, according to check the distribution whether normally distributed or not. The Chi-square test (X^2 -test) was also used to compare discrete random variables. Spearman's Rho correlation coefficient was used to find any relationship between two continuous variables. A p-value ≤ 0.05 was considered statistically significant.

4. Results

Total of 28 children, consisting of 18 girls (64.3%) and 10 boys (35.7%) aged 6–12 years were involved in this study. Mean age was 8.07 years with a standard deviation of 1.41 years. At the end of this study, a total of 56 injections were obtained for 28 children as NF injection (n = 28) and TM injection (n = 28).

In the study, when the distributions of the parameters (gender, type of dental treatment, type of teeth, and post-operative pain) were evaluated according to the type of injection technique, it was found that there was no statistically significant difference between the groups. (Table 1)

Table 1. Distribution of injection techniques based on evaluation parameters

Variables		Needle Free (NF) n	Traditional Method (TM) n	Total	p
Gender	Girl	18	18	36	1,000
	Boy	10	10	20	
Type of dental treatment	Filling	22	14	36	0,051
	Pulpotomy	6	14	20	
Type of teeth injected	1 st primary molar	12	7	19	0,259

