	2 nd primary molar	16	21	37	
Post-op pain (after one day)	Pain	5	7	12	0,746
	No pain	23	21	44	

*The Chi-square test (X^2 -test) was also used to compare discrete random variables.

Accordingly Table 2, in the group that received Needle-Free anesthesia in the first session and Traditional Method in the second session, the Wong-Baker scores were 4.44 ± 3.28 and 1.55 ± 0.88 , respectively. On the other hand, in the group that received Traditional Method anesthesia in the first session, the WB score was 1.68 ± 1.91 , while in the Needle-Free anesthesia group, the WB score was 2.52 ± 2.56 . In both cases, regardless of the method of anesthesia applied first, no statistically significant difference was found in the two groups. In the FLACC scores, for the Traditional Method - Needle Free group significant change was observed ($p = 0.025$) while for the Needle Free- Traditional Method group no statistically significant difference was observed ($p=0.141$). There were significant differences in the Amount of Anesthetic Solution (ml) and Duration of the Analgesia Effect (min) between the first and second visits for both injection methods, respectively as $p=0.003$ for NF-TM and $p<0.0001$ for

The Effect of Needle-free Injection System on Dental Injection Pain in Children: A Cross-over, Randomized Clinical Trial

TM-NF groups. The amount of anesthetic solution used for the 1st visit NF injection was $0,91\pm 0,48$ ml and $0,65\pm 0,30$ ml was for the 2nd visit NF injection. These amounts were statistically lower than TM injection in both visits. In the first visit, the mean duration of the analgesia effect in the NF group was 85.00 ± 39.05 min, whereas in the second visit, the mean duration for NF injection was found to be 90.26 ± 43.25 min. In the TM group, the mean anesthesia duration for the first and second visits was 140.00 ± 59.97 min and 130.00 ± 50.74 min, respectively. Regardless of the visit in which it was first applied, the duration of the analgesia effect in the NF group was found to be statistically significantly shorter than in the TM group ($p < 0,001$).

Table 2: Comparison of the 1st visit and 2nd visit measurements for continuous random variables in Needle Free-Traditional Method and Traditional Method - Needle Free

	1 st visit	2 nd visit	p
Wong Baker (WB) Scores			
Needle Free-Traditional Method	4,44±3,28	1,55±0,88	0,056
Traditional Method - Needle Free	1,68±1,91	2,52±2,56	0,119
FLAAC			

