Needle Free-Traditional Method	0,78±1,09	0,11±0,33	0,141
Traditional Method - Needle Free	0,21±0,41	0,68±0,67	0,025
Amount of Anesthetic Solution (ml)			
Needle Free-Traditional Method	0,91±0,48	1,62±0,38	0,003
Traditional Method - Needle Free	1,37±0,42	0,65±0,30	<0,0001
Duration of the Analgesia Effect (min)			
Needle Free-Traditional Method	85,00±39,05	130,00±50,74	0,001
Traditional Method - Needle Free	140,00±59,97	90,26±43,25	<0,001

*paired t-test was used

*Needle Free-Traditional Method group: 1st visit Needle Free and 2nd visit Traditional Method was used of injection.

*Traditional Method - Needle Free group: 1st visit Traditional Method and 2nd visit Needle Free was used of injection

Table 3: Wong-Baker and FLACC Scores in Needle Free-Traditional Method and Traditional Method - Needle Free groups based on gender

	Gender	Needle Free-Traditional Method Group		p	Gender	Traditional Method-Needle Free Group		p
		1 st visit Needle Free	2 nd visit Traditional Method			1 st visit Traditional Method	2 nd visit Needle Free	
Wong Baker	Girl N=6	4.1, (1.5-8.5)	2, (0-2)	0,141	Girl N=12	2, (0.5-2)	1, (0-3.5)	0,558
	Boy N=3	4.1, (2-4)	2, (2-2)	0,18	Boy N=7	0, (0-4)	2, (2-4)	0,059
FLACC	Girl N=6	0, (0-1.5)	0, (0-0.25)	0,414	Girl N=12	0, (0-0)	0.5, (0-1)	0,053
	Boy N=3	1, (0-1)	0, (0-0)	0,180	Boy N=7	0, (0-1)	1, (0-1)	0,317

*Wilcoxon nonparametric test was used

*Needle Free-Traditional Method group: 1st visit Needle Free and 2nd visit Traditional Method was used for injection.

*Traditional Method - Needle Free group: 1st visit Traditional Method and 2nd visit Needle Free was used for injection

* The values are presented as Median, (Inter Quartile Range)

In our study, which used a crossover design, we evaluated the effect of gender differences on Wong-Baker and FLACC scores for needle-free and traditional method injections administered

The Effect of Needle-free Injection System on Dental Injection Pain in Children: A Cross-over, Randomized Clinical Trial

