According to Spearman's Rho correlation coefficient test, no correlation was found between age and Wong Baker, FLACC scores, and the amount of anesthetic solution administered respectively ($p=0,830$, $p=0,436$, $p=0,976$). Similarly, no correlation was found between Wong Baker scores and the amount of anesthetic solution administered ($p=0,537$) and Wong Baker scores and the duration of the analgesia effect ($p=0,468$). However, a negative correlation was found between the FLACC score and the amount of anesthetic solution ($p=0,033$). Moreover a positive correlation was found between the FLACC score and Wong Baker scores as well as between the amount of dose administered and duration of analgesia effect respectively ($p=0,000$, $p=0,009$).

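### The FLACC–amount and amount–duration correlations are not shown to hold within a technique: if both techniques were pooled, the NF–TM difference is enough to produce them

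*Combined protocol and SAP*

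**What the plan says.** The Statistical Analysis section gives the method in one sentence: "Spearman's Rho correlation coefficient was used to find any relationship between two continuous variables". It mentions neither technique nor the two injections per child. The significance rule is "A p-value ≤ 0.05 was considered statistically significant".

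The last paragraph of 4. Results applies this. It states that "a negative correlation was found between the FLACC score and the amount of anesthetic solution" (p=0.033), and reports a positive correlation "between the amount of dose administered and duration of analgesia effect respectively" (p=0.009). No coefficient, interval or n accompanies either p-value.

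On the data available, 3.3 Procedure says: "A total of 56 procedures were performed and divided into 2 groups according to the anesthesia technique". Each of the 28 children contributes one NF and one TM injection.

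Separately, the text to Table 2 says that "the duration of the analgesia effect in the NF group was found to be statistically significantly shorter than in the TM group".

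**The concern.** Technique is associated with all three variables. In both sequences of Table 2, NF visits have a smaller amount, a higher FLACC score and a shorter duration than TM visits. If the two sets of visits are put in one scatterplot, they form two clusters. The line joining the clusters slopes down for FLACC against amount and up for duration against amount, even if amount is unrelated to either outcome inside each cluster.

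A reader who sees the bare correlations will probably take them to mean that more solution goes with less observed pain and longer analgesia. That reading needs a relation within a technique, and nothing reported addresses it.

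Two further points weaken the tests. Pooled p-values would treat 56 injections from 28 children as independent. And 3.4 Data collection has FLACC scored during the injection, whereas the amount (3.3.1 and 3.3.2) is the final total, including top-ups given later during treatment. A later top-up cannot have lowered a score already recorded.

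**Working it through.** **Inputs.** Table 2 means and SDs; sequence sizes 9 (NF first: 6 girls + 3 boys) and 19 (TM first: 12 + 7) from Table 3; p=0.033 and p=0.009 from 4. Results. Two-sided tests are assumed, as sidedness is not stated. Without rho or n, the reported p-values cannot be recomputed; they can only be converted.

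**1. Coefficients implied by the p-values.** |rho| = t/√(n−2+t²), with t the two-sided quantile on n−2 df.
- n=56, p=0.033: t=2.188, |rho| = 2.188/√(54+4.79) = 0.285.
- n=56, p=0.009: t=2.710, |rho| = 2.710/√(54+7.34) = 0.346.
- If n were 28, the values would be 0.40 and 0.48.

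**2. Means by technique, weighted by sequence size.**
- Amount: NF (9×0.91+19×0.65)/28 = 0.73 ml; TM (9×1.62+19×1.37)/28 = 1.45 ml.
- FLACC: NF (9×0.78+19×0.68)/28 = 0.71; TM (9×0.11+19×0.21)/28 = 0.18.
- Duration: NF (9×85.00+19×90.26)/28 = 88.6 min; TM (9×130.00+19×140.00)/28 = 136.8 min.

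**3. Correlation of each variable with technique (NF=1).** SDs are combined over the two sequences within a technique, then over all 56 injections. r = [(NF mean − TM mean)/2] × √(56/55) / total SD.

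| Variable | SD NF | SD TM | Total SD | r with NF |
|---|---|---|---|---|
| Amount (ml) | 0.379 | 0.418 | 0.536 | -0.675 |
| FLACC | 0.808 | 0.383 | 0.682 | +0.395 |
| Duration (min) | 41.3 | 56.4 | 54.7 | -0.445 |

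**4. Pooled correlation if there is no relation within technique.** This is the product of the two correlations with technique; p comes from t = r√(54/(1−r²)).
- FLACC–amount: 0.395 × (−0.675) = −0.27, p=0.047. Implied by the report: 0.285, negative.
- Amount–duration: (−0.675) × (−0.445) = +0.30, p=0.025. Implied by the report: 0.346, positive.

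**5. What is left after technique.** Partial r = (rho − r₁r₂)/√[(1−r₁²)(1−r₂²)].
- FLACC–amount: (−0.285+0.267)/√(0.544×0.844) = −0.03, p=0.85, 95% interval about −0.29 to 0.24.
- Amount–duration: (0.346−0.300)/√(0.544×0.802) = +0.07, p=0.62, interval about −0.20 to 0.33.

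These are approximate. They combine an implied Spearman coefficient with product-moment correlations and treat injections as independent.

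**6. Simulation on the rank scale.** In 4,000 trials of 56 injections, the four technique-by-sequence cells matched Table 2 and had no correlation inside any cell. Mean Spearman rho was −0.29 (95% range −0.52 to −0.04) for FLACC–amount and +0.30 (0.05 to 0.53) for amount–duration. With no within-technique relation, p<0.05 occurred in 60% and 63% of trials. Rebuilding the data another way (2,000 sets, permuting FLACC and duration within technique) gave −0.27 and +0.30, with 54% and 65% significant. The percentages depend on how the data are rebuilt; the mean correlations barely move.

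**The case against.** **Pooling is inferred.** No n or unit of analysis is given. Age has one value per child, so an analysis of 28 children is possible, and if a single technique was used the confounding argument falls away. This stands as a limit. Against it, Table 1 already counts injections as units (36 girls and 20 boys from 28 children), and a one-technique analysis would have needed the technique named.

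**Another reported pair fits less well.** Wong-Baker means are 3.14 (NF) and 1.64 (TM), giving r with NF of 0.309 and a technique-only correlation with amount of 0.309 × (−0.675) = −0.21. The reported p=0.537 implies |rho| of only 0.084 at n=56. In the 4,000-trial simulation, p was at least 0.537 in 27% of trials for this pair, so sampling error can explain the gap. It does not refute pooling, but it does not support it either.

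**Technique need not be the whole cause.** A reader might infer that the technique gap alone produced both correlations. Table 2 contains no within-technique correlations, and the intervals in step 5 allow values up to about 0.3 in size. Enough to produce them is as far as the evidence goes.

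**The document claims no dose-response.** It says only that correlations were found. The problem is what the bare statements invite, not a stated causal conclusion.

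**FLACC timing is not fully specified.** Scoring is not expressly limited to the first injection. Nor are top-ups clearly the larger part of the NF total. If the initial 0.1 ml is counted, they are (0.73−0.40)/0.73 = 45% of the mean; if not, (0.73−0.30)/0.73 = 59%. The timing argument needs only that a substantial part of the amount came later.

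**The duration comparison.** A reader might infer that the shorter NF duration is invalid because NF received half the amount (0.73/1.45 = 0.51). The documents do not support that. Amount was titrated to the child's response under each technique, so it is part of the technique as delivered. Citing the amount–duration correlation as proof that dose explains the gap would also rely on the very result questioned here. Within each technique, the sequence with the larger mean amount had the shorter mean duration (NF 0.91 ml, 85.0 min against 0.65 ml, 90.3 min; TM 1.62 ml, 130 min against 1.37 ml, 140 min). These are only four means, confounded with period.

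**Conclusion.** The point holds in limited form. If the two tests pool all 56 injections, as seems likely, technique-only correlations of about −0.27 and +0.30 match the sign and most of the size of the implied −0.285 and +0.346. Neither test is then evidence that amount is related to FLACC or duration within a technique, and their p-values also ignore the pairing within child. The conclusion rests on pooling, two-sided p-values, and Table 2 summaries standing in for individual data.

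Modest within-technique relations remain possible. The paired NF–TM comparisons, including that for duration, are unaffected.

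**What to change.** - State n, the unit of analysis and rho for every Spearman test in 4. Results.
- Replace the two tests with rho and a 95% interval within NF injections and within TM injections (28 each), or with the correlation of within-child NF-minus-TM differences (28 pairs). Either removes the technique gap and uses each child once per estimate. Label the re-analysis as post hoc.
- Drop or requalify the two statements if the relations do not persist, and say that FLACC was recorded during injection whereas amount is the final total.
- Keep the NF–TM duration result, described as the difference between techniques as delivered, including the amount each received. A dose-adjusted regression is not needed: amount is set after randomisation in response to the child, so adjustment would not separate device from dose cleanly.

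The cost is re-analysis of data already on the collection form, plus rewording. Intervals will be wider: the |rho| needed for p=0.05 rises from 2.005/√(54+2.005²) = 0.26 at n=56 to 2.056/√(26+2.056²) = 0.37 at n=28, so both significant results may disappear. The TM estimate for FLACC will be especially weak. TM scores total about 9×0.11+19×0.21 = 5 points, so at most five children scored above zero.
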